3.6.2 Outcomes for the model optimization phase

The main outcome of the design and optimization phase will be development of *the optimized implementation models* that achieves a high coverage and quality of iKMC and establish the norm of zero separation between the mother and her newborn in the four participating countries.

This will be measured through a primary coverage outcome in a tracer indicator that captures the skin-to-skin component of iKMC i.e., initiation and duration of skin-to-skin contact.

Primary coverage outcome: Proportion of preterm or LBW newborns requiring care in level 2 M-SNCUs) born in or brought to the iKMC implementing facility, within 24 hours of birth, who received iKMC. This will be captured through a tracer indicator on initiation and duration of skin-to-skin contact.

A baby is considered to have received iKMC if:

- Skin-to-skin contact is initiated within 2 hours after birth if the baby is born within the iKMC implementing facility, or within 2 hours of reaching the iKMC implementing facility if the baby is born outside the iKMC implementing facility (who reach the facility within 24 hours of birth) and
- Continuous skin-to-skin contact is provided by a mother/surrogate for at least 8 hours per day during the stay in the level 2 M-SNCU hospital (average hours per day for the overall M-SNCU stay)

Quality outcomes:

Proportion of preterm or LBW infants who arrived to an iKMC implementing facility within 24
hours after birth among those born in a health facility who required referred at birth to an iKMC
implementing facility

^{*}These neonates (except deceased newborns) will be excluded from the study for outcome measurement purposes however all newborns will receive appropriate care in the iKMC implementing facility.

- Proportion of preterm or LBW infants on respiratory support (any oxygen or CPAP) who received skin-to-skin contact > 8 hours/day in the M-SNCU
- Proportion of preterm or LBW infants receiving KMC at discharge (8-24 hours of skin-to-skin contact and exclusively breastfed) in the 24 hours before discharge from the iKMC implementing facility
- Proportion of preterm or LBW infants who are exclusively breastfed at discharge
- Median age at putting the baby to the breast for the first-time during M-SNCU stay

Implementation outcomes:

In the model optimization phase, we will also monitor the following implementation outcomes, including experience of care by mothers/caregivers and newborns:

- Acceptability: iKMC including transport in skin-to-skin contact from birthing place to M-SNCU is acceptable to mothers (and/or surrogates). Mothers and caregivers are satisfied with the care received. iKMC is acceptable to health workers (facility and community).
- *Adoption*: The challenges in adoption of iKMC by mothers, hospital managers and health providers (nurses, midwives, doctors) identified in programme learning are addressed.
- **Adaptation**: Modifications to adapt the iKMC intervention to the social and health system context are implemented.
- Fidelity: Quality iKMC care is provided to mothers and newborns in the level 2- M-SNCUs

Evaluation of the above outcomes and monitoring of the above implementation outcomes will increase our understanding of the challenges of scaling-up the intervention. The study will specifically provide us with experience of engaging multiple stakeholders, creating level 2 M-SNCUs and making them functional, fostering collaboration between obstetric and paediatric departments, and changing policies to allow iKMC implementation.

3.7 Scale up of the optimized implementation model in stepped-wedge trial phase

During this phase, the optimized iKMC implementation model will be implemented in a randomized stepped-wedge manner in 3 clusters across the three districts to evaluate its effectiveness on neonatal outcomes.

Each cluster would be one health administrative unit of district/sub-district with at least 1-2 health facilities having a functional level 2 SNCU. The characteristics of the study sites are described in section 3.2. The health facilities having a functional level 2 SNCU in all the three districts in Uttar Pradesh will be supported to become iKMC implementing facilities by strengthening the quality of preterm and LBW newborn care to ensure a minimum package of care for small and sick newborns prior to their randomization for this effectiveness evaluation. Preparatory work for setting up M-SNCUs, including identification of space and organization of infrastructure, procurement of KMC supplies, and training of existing health workers will be done during this time. The process of institutionalizing monitoring and evaluation will also be started wherein process and outcome indicators will be incorporated in the Health Management Information System to be reviewed periodically by all stakeholders to ensure accountability, sustainability, and scalability.

3.7.1. Strengthening care for preterm or LBW babies in districts

Health facilities with level-2 SNCUs in the three identified districts will be assessed for their ability to provide essential childbirth care for all newborns and WHO minimum package of care for small and sick newborns (see Annex 1). The identified gaps will be addressed by the study team in collaboration with the government and facility administration. Staff will be trained to provide quality routine intrapartum care, essential newborn, and preterm birth care (including care at birth, thermal care, KMC, feeding support, respiratory support including CPAP, and prevention and treatment of infection). Governments will ensure that all necessary supplies and equipment are available. During the time frame that the model is being developed and

optimized in one study area per site, the activities to strengthen the SNCUs in the potential iKMC implementing facilities will be initiated in the other study areas. This will be done in one district and will be concluded before the scale-up effectiveness evaluation is launched and the optimized iKMC model is implemented.

3.7.2 Evaluating the impact of the scale-up: stepped-wedge cluster RCT design

The impact of the scale-up of the optimized model on neonatal mortality will be evaluated in a stepped-wedge, cluster-randomised trial design in 3 districts over a 24-month duration (Figure 8). The unit of randomization will be a district with 1-2 facilities having functional level 2-SNCUs that provide a minimum package of small and sick newborn care. Each cluster will be randomized sequentially to implement the optimized iKMC model.

Figure 10. Roll-out of the stepped wedge cluster RCT design in UP

#	Υ0	Y1-Q1	Y1-Q2	Y1-Q3	Y1-Q4	Y2-Q1	Y2-Q2	Y2-Q3	Y2-Q4
Cluster 1	Minimum	С	т	1	1	1	I	ı	1
Cluster 2	Care Package for small babies	С	С	С	Т	ı	ı	ı	ı
Cluster 3	implemented	С	С	С	С	С	т	ı	1

C= Refers to control period in which small or sick newborn care is strengthened.

T= Refers to transition period (no measurement)

I= Refers to intervention period in which the iKMC implementation model scaled up

The stepped-wedge design is a unidirectional crossover design where all clusters start in the control phase (i.e., minimum package of care for small and sick newborns) and cross over to the intervention (i.e., the optimized iKMC implementation model) at different timepoints, till all clusters have transitioned to the intervention condition. All 3 clusters in the state will start with the control condition (see Figure 10). At each equally spaced cross-over time, one cluster will transition to the immediate KMC implementation model based on a pre-allocated random sequence. A three-month transition period is included in each cluster to allow for the implementation model to be operationalized. All the implementation strategies which are part of the optimized model will be implemented during this period. Briefly, these will include infrastructural changes (e.g., M-SNCUs), supplies (e.g. KMC beds, chairs, and garments), staff training and supervision, monitoring and feedback in the immediate KMC implementing facilities, and strengthening of newborn care to ensure early identification and referral of eligible infants to the immediate KMC implementing facility in skin-to-skin contact with the mother or surrogate, and strengthening of referral pathways. Once each cluster has crossed to the intervention, it will continue to be exposed to it for the remaining duration of the study. The coverage outcomes will be analyzed at the state and country level (along with another similarly designed study to be conducted in Haryana). However, impact outcomes, i.e., pre-discharge and neonatal mortality will be pooled and analyzed at the country level (along with another similarly designed study to be conducted in Haryana) and ascertained at a global level in combination with data from multiple countries by the WHO.

The rationale for a stepped-wedge design in evaluating the effectiveness of the optimized implementation model is as follows:

- There are clear benefits to the use of iKMC for newborns. Therefore, it is important for the governments/ ministries /policymakers and the local healthcare providers involved in this implementation research study to be assured that no districts/patients are denied improved access to iKMC because of being part of a research project. Through this design, they can participate in a randomized trial and all clusters can be guaranteed to receive the intervention.
- The optimized iKMC implementation model is a complex service delivery intervention. The step wedge design takes advantage of the logistical needs of delivering a complex service delivery intervention, by rolling this out in a staggered fashion to all participating sites.
- The design ensures a randomized comparison group is available to generate high-quality evidence when time trends are taken into account.

3.7.3. Randomization

The study will run concurrently in the 6 clusters in 2 sites of India i.e. 3 clusters in UP (by CEL) site and 3 in Harvana (by SAS). The clusters will be the unit of randomization. In addition to the criteria for site selection

described in section 3.2.1, the clusters should have made an in-principle commitment to implementing the iKMC optimized model components according to the schedule assigned by the randomized allocation scheme (i.e., stepped-wedge design).

Prior to trial commencement, all clusters will be randomly assigned to one of the sequences for the time from the control period to the intervention period, using a computer-generated list of random numbers (generated by the study statistician). Investigators and study teams will remain blinded to this allocation sequence. The next clusters to be randomized will only be revealed approximately 3 months prior to each cross-over timepoint, to provide adequate time for the preparation of iKMC model implementation.

3.7.4. Trial facilities and trial participants

The trial facilities will be facilities having a functional level 2 SNCU. There should be at least one such facility in each of the study clusters. The trial participants will be preterm or LBW infants requiring care in the SNCU of the trial facilities, either born alive or brought alive to the trial facilities within 24 hours of birth, as per the inclusion and exclusion criteria in section 3.6.1. While the study will promote and strengthen immediate KMC for all preterm or LBW infants, the study population will only comprise preterm or LBW infants who require SNCU admission after birth as depicted in Figure 6.

Intervention

The intervention would be the optimized iKMC implementation model in each site. Core component of the intervention is the conversion of level 2 SNCU to level 2 M-SNCU in trial facilities during the intervention period. Preterm or LBW infants who require SNCU admission after birth, as depicted in Figure 6, will be admitted to M-SNCU where mother/surrogate will stay with the newborn on 24x7 basis and supported to provide KMC.

Control

Usual care (minimum package of care for small and sick newborns including KMC) will be provided to preterm or LBW babies during the control period. Preterm or LBW infants requiring SNCU care will be admitted to the SNCU.

Both groups: In both intervention and control period, most preterm or LBW infants will go to the postnatal or KMC wards after discharge from the SNCU/M-SNCU and will continue KMC until discharge from the trial facilities.

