We have established the Partnership for Research in Advancing Maternal and Newborn Health (PRAMAAN) – a consortium of public and private medical colleges and institutions that are keen to apply evidence-based and data-driven approaches to institutionalize KMC for all LBW and preterm infants within their facilities, and support the state in its scale-up. Ten medical colleges in UP are already part of this consortium. This consortium will serve as a strong research platform for future studies/ implementation research related to maternal and newborn health.

We will typically choose districts that have a combination of a well-established medical college with a fully functional NICU along with a district hospital with a reasonably well-performing SNCU, and pediatric and obstetric teams that have the eagerness and capacity to institutionalize KMC within their facilities. This is in line with UP's plan to have a medical college in each district. Further, the medical college can support the district hospital and other facilities along the referral chain in institutionalizing iKMC. After the study, the participating districts and facilities will serve as dissemination and training centers for immediate KMC integration for other districts in their region.

At a district level, we will establish close working partnerships between the medical college and the district hospital, to leverage local expertise of medical colleges in establishing systems and strengthening quality of care in district hospitals. Similarly, close working partnerships will be encouraged between district facilities and community health centers. This would facilitate greater integration, accountability and referral between these entities and improved quality of care for newborns overall, in the chosen districts.

2. Implementation Research Objectives

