3.1 Study design

This study will be part of a multi-country implementation research and effectiveness study to improve care for preterm or LBW babies. The study will be conducted in two phases. In phase I, the implementation model will be developed through an iterative co-development process with involvement of key stakeholders in chosen facilities in one district. In phase II, the implementation model will be scaled up across 3 additional districts in UP, and the impact on neonatal mortality and other important outcomes will be evaluated.

Phase I is the model development and optimization phase. To develop and optimize the implementation model, we will use a mixed-methods design that applies both qualitative and quantitative research methodologies. Formative research will be used to identify barriers and facilitators for quality iKMC to design the initial implementation model. Concurrent programme learning using qualitative research and outcome measurement while implementing the model in routine care settings will be used to improve the model iteratively until high coverage of quality iKMC is achieved. The final (optimized) implementation model will be scaled up across 3 additional districts in UP using a stepped-wedge design as part of Phase II, to evaluate the impact of this scale up on neonatal mortality and other important outcomes.

[figure not shown]
We will choose the Phase I district from central UP in alignment with the high-level strategy. The Phase II districts will be chosen to ensure regional representation across UP, and therefore we will choose at least one district from western and eastern UP regions (see Figure 5). Objective criteria for choosing the study districts include: (i) admission rate of <1800 gram infants in NICU-SNCU combination of >= 45 per month, (ii) overall NMR in <1800 gram infants of >= 15%.

Figure 4 – Overview of the study

We will align with the Every Newborn Action Plan (ENAP) ²⁷ levels of care detailed in Annex 1, and include activities required to implement iKMC at level 1 (primary, essential newborn care), level 2 (secondary, special newborn care), and level 3 (tertiary care, intensive newborn care), where applicable.

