3.3 Study population

Newborns: The study population is preterm or LBW newborns (gestational age <37 weeks or birthweight<2.5 kg) (requiring care in the SNCU, i.e., weighing <1800 grams at birth, or those preterm or LBW newborns who weigh >=1800 grams but are sick and need SNCU admission. See Figure 6 below.

The revised WHO guidelines include a recommendation for KMC for all preterm or LBW infants starting immediately after birth unless the newborn is critically sick.²⁶ Therefore, KMC provision for all preterm or LBW infants will be strengthened at all levels of care.

However, the purpose of the study is to implement and scale up iKMC for preterm or LBW infants **who are at high risk of being separated from the mother**, i.e., those preterm or LBW infants who require NICU/SNCU care, either because they are too small or sick. Hence, while the study will promote and strengthen immediate KMC for all preterm or LBW infants, the study population will only comprise of preterm or LBW infants who require NICU/SNCU admission after birth as depicted in Figure 6. During the intervention period, these infants will be admitted to M-NICU/SNCUs where their mother/surrogate will stay with them on a 24x7 basis and will be supported to provide KMC. During the control periods, these infants will be admitted to the normal/routine NICU/SNCU and KMC will be promoted and encouraged through existing mechanisms.

Figure 6 - Description of study population

The population eligible for outcome evaluation is described in Section 3.6.1

Health workers: Health workers (and managers) working at the participating sites will be the target of community-, facility- and provider-level components of the iKMC implementation models.

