We will strengthen the existing clinical record keeping in the SNCUs and the use of a separate SNCU register wherein the routine SNCU staff will record the key secondary outcomes like breastfeeding clinical sepsis, hypothermia, and hypoglycaemia. During the daily visits, the study evaluation team will cross-verify the entries in the SNCU register using the clinical records and healthcare provider and/or maternal interviews. The optimal strategy will be worked out during the preparatory phase. For documentation of continued KMC post-discharge, the outcome evaluation team will administer a pre-tested questionnaire to the mother telephonically on day 29. Documentation of iKMC implementation will be similar as in the model optimization phase.

Detailed information on definitions, numerator, and denominator for each outcome in the model optimization phase is described in the Table 4, however it is important to note that the measurement strategy for the secondary outcomes will be refined based on the learnings from the model optimisation phase.

Table 4. Definitions, numerators, and denominators of outcomes in stepped-wedge trial phase

Table 4. Delimitions, numerators,	and denominators of out	отпев ит втерреи и	eage that phase	
	Numerator and denominator	Specific notes to the	Data collected by	
		indicator	Who	How and where
Primary outcome to be measi	ured in both intervention	and control perio	ods for each stu	dv cluster
Proportion of preterm or LBW infants who died during the first 28 days of life (among trial participants)	Numerator: Number of neonatal deaths by 28 days of age Denominator: Number of preterm or LBW infants admitted in the M-SNCU/SNCU in the trial facilities (Expressed as percentage or rate per 1000 livebirths)		Outcome evaluation team	By daily visits to M- SNCU/SNCU until discharge, and through telephone contact on day 29 of age post- discharge
Secondary outcomes to be m measurement strategy will be	easured in both interver			study cluster (the
Breastfeeding outcomes:			First outcome will be	Using hospital registers and
Proportion of preterm or LBW infants who are exclusively breastfed at discharge from trial facilities	Numerator: Number of preterm or LBW infants who are exclusively breastfed Denominator: Number of preterm or LBW infants admitted		measured by the outcome evaluation team	maternal interviews

	Numerator and denominator	Specific notes	Data	collected by
	denominator	indicator	Who	How and where

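### Trial participants are defined by need for SNCU care, but the primary denominator and vital-status visits by admission to the SNCU/M-SNCU, so it is unclear whether an eligible infant in a separate NICU is counted

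*Protocol*

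**What the plan says.** Section 3.3 describes the population in two ways. Its opening definition is by need: "requiring care in the SNCU, i.e., weighing <1800 grams at birth", or heavier but sick. It then says "the study population will only comprise of preterm or LBW infants who require NICU/SNCU admission after birth as depicted in Figure 6". Section 3.7.4 repeats that sentence and cites the same figure, but without the NICU: "the study population will only comprise preterm or LBW infants who require SNCU admission after birth as depicted in Figure 6". Its participant definition is again by need: "The trial participants will be preterm or LBW infants requiring care in the SNCU of the trial facilities".

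Section 3.7.5 makes section 3.6.1 the governing population, and 3.6.1 is also worded as requiring SNCU care. In section 4.2.3, Table 4 labels the primary outcome as being among trial participants but gives it this denominator: "Denominator: Number of preterm or LBW infants admitted in the M-SNCU/SNCU in the trial facilities". Sections 3.7.6 and 4.2.3 collect vital status on infants admitted to SNCUs, through daily visits to those units and later telephone contact.

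On facilities, section 3.2.2 puts at least one medical college in every Phase II district. Section 1.1.1 describes a medical college's unit as a Level 3 NICU, distinct from the Level 2 SNCU of a district-level hospital. Section 1.2 seeks districts with "a well-established medical college with a fully functional NICU along with a district hospital with a reasonably well-performing SNCU". Section 3.1 selects districts on an "admission rate of <1800 gram infants in NICU-SNCU combination of >= 45 per month".

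**The concern.** The primary outcome is a proportion, so the rule for entering the denominator has to be the same in control and intervention periods and must not depend on anything the intervention changes. Here the participant definition depends on the infant's condition and the denominator on the unit of admission. The intervention consists largely of converting that unit.

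Physicians at the facility identify and triage infants (section 4.1.2) and cannot be blind to a converted unit. If unstable infants were more often placed in a separate NICU after crossover, mortality in the M-SNCU would fall with no lives saved. If the M-SNCU took infants formerly kept in a NICU, a real benefit would be partly hidden. Analysing clusters by randomised crossover time, as section 3.7.7 plans, does not repair differential entry of individual infants.

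**Working it through.** **1. The definitions side by side.**

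| Place | Basis | Units named |
|---|---|---|
| 3.3, opening definition | need (<1800 g, or heavier and sick) | SNCU |
| 3.3, later sentence | need | NICU/SNCU |
| 3.6.1 | need | SNCU |
| 3.7.4, participants | need | SNCU |
| 3.7.6 and 4.2.3, vital status | admission | SNCU |
| 4.2.3, permission for day-29 follow-up | need | SNCU |
| Table 4, primary denominator | admission | M-SNCU/SNCU |

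The basis changes between 3.7.4 and Table 4, and even within 4.2.3. M-NICUs, which objective 1 in section 2.1 says will be created, are not in the Table 4 denominator.

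**2. Trace one infant.** Take a 1,500 g infant on CPAP, breathing spontaneously, with no malformation and no shock. No exclusion listed in 3.6.1 applies. The infant is under 1800 g, so it requires SNCU care under 3.3 and is a participant under 3.7.4. CPAP is listed among NICU services in 1.1.1 and among M-SNCU provisions in 3.5.1, so the description of care does not settle the unit. If admitted to the SNCU or M-SNCU, the infant is in the denominator and seen at daily visits. If admitted only to a separate NICU, the infant is in neither, although still a participant.

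**3. The plan's own figures.** Target: 0.15 × (1 − 0.20) = 0.12, as stated. Total: 24 clusters × 500 per year × 2 years = 24,000, as stated. The protocol gives neither the share of eligible infants placed in a NICU nor their mortality, so the effect of the wording on the RR or on power cannot be derived from it.

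**4. Illustration with assumed inputs.** Let x be the share of eligible infants placed in a NICU in intervention periods only, and m their mortality. Overall mortality is 15% in both periods, so there is no true effect. Then

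observed intervention mortality = (0.15 − x·m) / (1 − x), and apparent RR = that value / 0.15.

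| x | m | Calculation | Observed mortality | Apparent RR | RR if the loss is in control periods only |
|---|---|---|---|---|---|
| 5% | 30% | 0.135/0.95 | 14.2% | 0.95 | 1.06 |
| 5% | 40% | 0.130/0.95 | 13.7% | 0.91 | 1.10 |
| 10% | 30% | 0.120/0.90 | 13.3% | 0.89 | 1.13 |
| 10% | 40% | 0.110/0.90 | 12.2% | 0.81 | 1.23 |

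The last column is the reciprocal: 0.15 divided by the observed mortality. Two conditions are needed for any bias. If x and m are equal in both periods, the ratio is 1. If m = 15%, observed mortality is (0.15 − 0.15x)/(1 − x) = 15% and the ratio is again 1.

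**The case against.** The strongest reply is that no separate NICU is shown. Objective 1 (section 2.1) and sections 3.5.1, 3.5.4 and 3.5.7 use level 2 NICU for the unit to be converted or strengthened. Section 1.1.1 speaks of newer colleges moving from level 2 to level 3, which reads as one unit changing level. The medical-college hospital in section 3.2.1 is itself counted as having an SNCU. No section places a NICU beside a level 2 SNCU in one trial hospital. This stands: the gap opens only where a trial facility has a separate NICU, and a reader might wrongly infer that college NICU infants are certain to drop out of the outcome.

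Second, the definition in 3.7.4 is by need, so it does not itself exclude such an infant. That is correct, and it places the conflict more exactly, between 3.7.4 and Table 4. The day-29 permission step in 4.2.3 is also by need, so some of these infants might still be followed by telephone. Table 4 would not count them.

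Third, 3.6.1 excludes early shock and early invasive ventilation in both periods, which removes the clearest intensive-care cases. Provider aversion in section 1.2 is given as a reason for choosing early adopters, and section 3.7.3 requires cluster commitment. These points reduce the likely shift but do not fix the rule.

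Fourth, Figure 6, cited in both 3.3 and 3.7.4, is not visible in the text at hand and may name the units. It could clarify the population, but the Table 4 wording would still need to match it. Standard case report forms (section 4.3) harmonise data only once the definition is settled.

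**Conclusion.** The point holds as an inconsistency in who is counted in the primary outcome. Participation is by need in 3.7.4 and 3.6.1, the denominator and vital-status visits are by unit of admission, and NICU is used both for a separate Level 3 unit and for the unit to be converted. Where a trial facility has a separate NICU, the stated denominator depends on a placement made by staff who know the exposure, and the mortality comparison can be biased either way.

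The size is unknown. The range of 0.81 to 0.95 shows only what assumed shifts of 5% to 10% and assumed mortalities of 30% to 40% would do. The upper end of those assumptions is close to the target RR of 0.80, but it is not an estimate. A reader might infer that selection bias will occur or that it could account for the whole planned effect. The protocol supports neither, because it documents no separate NICU in a trial hospital, no shift in placement and no NICU mortality.

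**What to change.** Reconcile sections 3.3, 3.6.1, 3.7.4, 3.7.6 and 4.2.3 with Table 4, and check them against Figure 6. Participants, vital-status follow-up and the primary denominator should all be the same set: infants who meet 3.6.1, are born in or brought to a trial facility within 24 hours of birth, and are admitted to any of its newborn units (SNCU, M-SNCU, NICU or M-NICU). Apply this identically in control and intervention periods. Record the unit of first admission and report its distribution by period, so that any shift at crossover can be seen. State once how NICU and SNCU are used.

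The cost is protocol wording and, where a separate NICU exists, extending the daily visits to another unit of the same hospital. Some counted infants will not have been in the converted unit, which dilutes the effect slightly, as intention to treat implies. The change concerns who is counted and prescribes no clinical placement. It should be settled before enrolment, because infants not followed from the start may not be recoverable.
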